### 2 STUDY OBJECTIVES

# 2.1 Primary Objective

The primary objective of this study is to evaluate the effect of objectrapib in combination with ezetimibe compared to placebo on LDL-C at Day 57.

# 2.2 Secondary Objectives

The secondary objectives of this study include the following:

- To evaluate the effect of obicetrapib monotherapy compared to placebo on LDL-C at Day 57;
- To evaluate the effect of obicetrapib in combination with ezetimibe compared to placebo on ApoB at Day 57;
- To evaluate the effect of obicetrapib monotherapy compared to placebo on ApoB at Day 57;
- To evaluate the effect of obicetrapib in combination with ezetimibe compared to ezetimibe monotherapy on LDL-C at Day 57;
- To evaluate the effect of obicetrapib monotherapy compared to ezetimibe monotherapy on LDL-C at Day 57;
- To evaluate the effect of ezetimibe monotherapy compared to placebo on LDL-C at Day 57;
   and
- To evaluate the effect of obicetrapib in combination with ezetimibe compared to ezetimibe monotherapy on ApoB at Day 57.

# 2.3 Exploratory Objectives

The exploratory objectives of this study include the following:

- To evaluate the effect of ezetimibe monotherapy compared to placebo on ApoB at Day 57;
- To evaluate the effect of obicetrapib alone, ezetimibe alone, and obicetrapib in combination with ezetimibe on non-HDL-C, VLDL cholesterol (VLDL-C), HDL-C, TG, apolipoprotein E (ApoE), and HDL-ApoE (with and without apolipoprotein C3 [ApoC3]) at Day 57;
- To evaluate the effect of obicetrapib alone, ezetimibe alone, and obicetrapib in combination with ezetimibe on the proportion of participants achieving predefined LDL-C targets at Day 57;
- To assess the mean trough plasma levels of obicetrapib alone, ezetimibe alone, and obicetrapib in combination with ezetimibe at steady state on Day 57, Week 12, and Week 16;
- To evaluate the effect of obicetrapib alone, ezetimibe alone, and obicetrapib in combination with ezetimibe on CETP mass at Day 57, Week 12, and Week 16; and
- To evaluate the safety and tolerability profiles of obicetrapib alone, ezetimibe alone, and obicetrapib in combination with ezetimibe assessed by clinical laboratory values and incidence of AEs.

### 3 STUDY DESCRIPTION

# 3.1 Summary of Study Design

This study will be a placebo-controlled, double-blind, randomized Phase 2 study in participants with mild dyslipidemia to evaluate the efficacy, safety, and tolerability of obicetrapib and ezetimibe combination therapy. The study will take place at approximately 10 to 15 sites in North America and Europe as appropriate.

The population for this study includes men and women 18 to 70 years of age, inclusive, with a body mass index <40 kg/m^2 and mild dyslipidemia defined as fasting LDL-C levels >2.5 mmol/L (>100 mg/dL) and <4.5 mmol/L (<175 mg/dL) and TG levels <4.5 mmol/L (<400 mg/dL).

# 3.1.1 Screening Period

At the Screening Visit (Visit 1), participants will be required to sign an informed consent form (ICF) before any study-related procedures are performed. After signing the ICF, participants will be assessed for study eligibility. Participants will also receive counselling regarding the Therapeutic Lifestyle Changes (TLC) diet and will receive instructions on how to follow this diet (see Appendix C). Participants will be required to begin the diet starting at the Screening Visit.

#### 3.1.2 Treatment Period

Up to 2 weeks after the Screening Visit, participants will return to the site on Day 1 (Visit 2) to be randomized and begin treatment. Approximately 100 eligible participants (25 participants per treatment group) will be randomized in a 1:1:1:1 ratio to 1 of the following treatment groups:

- Combination therapy: 5 mg obicetrapib + 10 mg ezetimibe;
- Obicetrapib monotherapy: 5 mg obicetrapib + placebo ezetimibe;
- Ezetimibe monotherapy: placebo obicetrapib + 10 mg ezetimibe; or
- Placebo: placebo obicetrapib + placebo ezetimibe.

During the 8-week Treatment Period, the assigned study drugs will be administered by the participant orally and once daily on Days 1 through 57. Participants will return to the site every 4 weeks for efficacy, safety, PK, and CETP mass assessments. Participants, Investigators, the Clinical Research Organization, and the Sponsor will be blinded to all lipid results from Day 1 (Visit 2) for the first participant through the PK Visit (Visit 6) for the last participant in order to protect blinding to treatment assignment.

#### 3.1.3 Safety Follow-up Period

Participants will return to the site for a Safety Follow-up Visit (Visit 5) approximately 4 weeks after the end of the Treatment Period for safety, PK, and CETP mass assessments.

#### 3.1.4 Pharmacokinetic Period

Participants will return to the site for a PK Visit (Visit 6) approximately 8 weeks after the end of the Treatment Period for PK and CETP mass assessments.

# 3.2 Study Indication

The indication for this study is mild dyslipidemia.

#### 4 SELECTION AND WITHDRAWAL OF PARTICIPANTS

#### 4.1 Inclusion Criteria

Participants who meet all of the following criteria will be eligible to participate in the study:

- 1. Understanding of the study procedures, willingness to adhere to the study schedules and diet, and agreement to participate in the study by giving written informed consent prior to Screening procedures;
- 2. Men or women 18 to 70 years of age, inclusive;
  - o Women may be enrolled if all 3 of the following criteria are met:
    - They are not pregnant;
    - They are not breastfeeding; and
    - They do not plan on becoming pregnant during the study;
  - O Women of childbearing potential must have a negative urine pregnancy test at the Screening Visit. Note: Women are not considered to be of childbearing potential if they meet 1 of the following criteria as documented by the Investigator:
    - They have had a hysterectomy or tubal ligation at a minimum of 1 cycle prior to signing the ICF; or
    - They are post-menopausal, defined as ≥1 year since their last menstrual period for women ≥55 years of age or ≥1 year since their last menstrual period and have a follicle-stimulating hormone (FSH) level in the menopausal range for women <55 years of age;

  - O Women of childbearing potential must agree to use an effective method of avoiding pregnancy from the Screening Visit to 90 days after the last visit. Men whose partners are of childbearing potential must agree to use an effective method of avoiding pregnancy from the Screening Visit to 90 days after the last visit. Effective methods of avoiding pregnancy are contraceptive methods with a Pearl index of <1 used consistently and correctly (including implantable contraceptives, injectable contraceptives, oral contraceptives, transdermal contraceptives, intrauterine devices, diaphragm with spermicide, male or female condoms with spermicide, or cervical cap) or a sterile sexual partner;
- 3. Fasting LDL-C levels >2.5 mmol/L (>100 mg/dL) and <4.5 mmol/L (<175 mg/dL) and TG levels <4.5 mmol/L (<400 mg/dL) (Visit 1); and
- 4. Willingness to maintain a stable diet and physical activity level throughout the study.

#### 4.2 Exclusion Criteria

Participants who meet any of the following criteria will be excluded from participation in the study:

- 1. Body mass index  $\geq 40 \text{ kg/m}^2$ ;
- 2. Participation in another clinical study involving an investigational or marketed drug within 30 days prior to the Screening Visit;
- 3. Currently taking any lipid-altering therapy;

- 4. Any clinical manifestation of atherosclerotic CVD or any evidence of ischemic coronary disease present on the 12-lead ECG at the Screening Visit;
- 5. Diagnosis of type 1 or type 2 diabetes mellitus; or glycosylated hemoglobin (HbA1c) ≥6.5% at the Screening Visit if no prior diagnosis of diabetes mellitus;
- 6. Uncontrolled hypertension, ie, sitting systolic blood pressure >160 mmHg and/or sitting diastolic blood pressure >90 mmHg taken as the average of triplicate measurements. One retest will be allowed, at which point if the retest result is no longer exclusionary, the participant may be randomized:
- 7. Active muscle disease or persistent creatine kinase concentration >3 × the upper limit of normal (ULN). One retest will be allowed after 1 week to verify the result, at which point if the retest result is no longer exclusionary, the participant may be randomized;
- 8. History of torsades de pointes;
- 9. Estimated glomerular filtration rate <60 mL/min calculated using the Chronic Kidney Disease Epidemiology Collaboration equation;
- 10. Hepatic dysfunction as evidenced by any laboratory abnormality as follows: gamma-glutamyl transferase, alanine aminotransferase, or aspartate aminotransferase >2 × ULN, or total bilirubin >1.5 × ULN;
- 11. Anemia, defined as hemoglobin concentration <11 g/dL for males and hemoglobin concentration <9 g/dL for females;
- 12. History of malignancy within the past 5 years, with the exception of non-melanoma skin cancers;
- 13. Evidence of any other clinically significant non-cardiac disease or condition that, in the opinion of the Investigator, would preclude participation in the study; or
- 14. Known ezetimibe or CETP inhibitor allergy or intolerance.

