#### 4.5 Withdrawal Criteria

Participation in this clinical study may be discontinued for any of the following reasons:

- The participant withdraws consent or requests discontinuation from the study for any reason;
- Occurrence of any medical condition or circumstance that exposes the participant to substantial risk and/or does not allow the participant to adhere to the requirements of the protocol;
- Any SAE, clinically significant AE, severe laboratory abnormality, intercurrent illness, or other medical condition which indicates to the Investigator that continued participation is not in the best interest of the participant;
- Pregnancy;
- Requirement of prohibited concomitant medication;
- Participant failure to comply with protocol requirements or study-related procedures; or
- Termination of the study by the Sponsor or the regulatory authority.

If a participant withdraws prematurely from the study due to the above criteria or any other reason, study staff should make every effort to complete the full panel of assessments scheduled for the Early Termination Visit. The reason for participant withdrawal must be documented in the electronic case report form (eCRF).

In the case of participants lost to follow-up, at least 3 attempts to contact the participant must be made and documented in the participant's medical records.

Withdrawn participants will not be replaced.

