# 5.3 Randomization and Blinding

Participants who meet all eligibility criteria will be randomized into the study. Participants will be randomized in a 1:1:1:1 ratio to the combination therapy, obicetrapib monotherapy, ezetimibe monotherapy, or placebo treatment groups. At randomization, participants will be stratified according to their Screening Visit (Visit 1) LDL-C value (<3.5 mmol/L [<135 mg/dL] or ≥3.5 mmol/L [≥135 mg/dL]). An automated interactive response technology (IRT) system will be used to assign the participant to 1 of the 4 treatment groups.

Participants, Investigators, the Clinical Research Organization, and the Sponsor will be blinded to all lipid results from Day 1 (Visit 2) for the first participant through the PK Visit (Visit 6) for the last participant in order to protect blinding to treatment assignment.

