# 8.10 Electrocardiograms

A single, standard 12-lead ECG will be performed by the Investigator or trained site personnel at the Screening Visit and centrally read by

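### Exclusion criterion 13 limits general investigator judgement to non-cardiac disease, so significant non-ischaemic heart disease other than torsades meets no exclusion that clearly applies

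*Protocol*

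**What the plan says.** Protocol Section 4.2 lists 14 exclusion criteria. The last but one, criterion 13, is the only one that turns on the investigator's general judgement: "Evidence of any other clinically significant non-cardiac disease or condition that, in the opinion of the Investigator, would preclude participation in the study".

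Three other criteria are cardiovascular:

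- Criterion 4: "Any clinical manifestation of atherosclerotic CVD or any evidence of ischemic coronary disease present on the 12-lead ECG at the Screening Visit".
- Criterion 6: "Uncontrolled hypertension, ie, sitting systolic blood pressure >160 mmHg and/or sitting diastolic blood pressure >90 mmHg", taken as the average of three readings, with one retest.
- Criterion 8: "History of torsades de pointes".

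Section 5.3 then makes entry depend on the list: "Participants who meet all eligibility criteria will be randomized into the study".

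Section 4.5, on withdrawal, is worded more widely. One ground for ending participation is "Occurrence of any medical condition or circumstance that exposes the participant to substantial risk". Another is any other medical condition that leads the investigator to think continuing is not in the participant's best interest. Neither is restricted to non-cardiac disease.

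**The concern.** A residual clause limited to non-cardiac disease fits comfortably beside the rest of the list only if the named criteria already deal with cardiac disease, or if the sponsor meant them to be a closed list. They do not deal with all of it, and the protocol does not say that the list is closed.

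Heart failure or cardiomyopathy of non-ischaemic origin, valve disease, and rhythm or conduction disorders other than torsades are examples of what falls between the criteria. An investigator who thinks that taking part would be unsafe for such a person has no criterion that plainly supports exclusion.

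Two things are at stake. The first is participant protection at entry. The second is consistency: with approximately 10 to 15 sites planned, one investigator could enrol such a person while another turns the same kind of person away with no criterion to cite.

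**Working it through.** The plan states no figure on this point and no arithmetic applies. The check is a reading of every place that could supply an entry rule.

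1. **Inclusion criteria (Section 4.1).** The four criteria concern consent and adherence, age and childbearing, lipid levels, and stable diet and activity. None requires absence of heart disease.

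2. **Exclusion criteria (Section 4.2).** Of the 14, criteria 4, 6 and 8 are cardiovascular and criterion 13 is the catch-all. The other 14 − 3 − 1 = 10 concern body mass index, other studies, lipid-altering therapy, diabetes, muscle disease, renal function, liver tests, anaemia, malignancy and drug allergy or intolerance. None of the ten reaches heart disease.

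3. **What the three cardiovascular criteria cover.** Criterion 4 catches heart disease that is a manifestation of atherosclerotic disease, and ischaemic coronary disease seen on the screening ECG. Criterion 6 is a blood-pressure threshold. Criterion 8 is one arrhythmia. The uncovered area is therefore clinically significant heart disease that is non-atherosclerotic, non-ischaemic and not torsades.

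4. **Whether criterion 13 reaches that area.** On its natural reading, *non-cardiac* qualifies both nouns that follow it, and the area is left out. If it qualifies only the first noun, a cardiac condition could still be brought in under the second. The text does not settle this, so investigator discretion over cardiac disease is not clearly given. It cannot be said to be clearly withheld.

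5. **Other sections.** Retesting (4.3) and rescreening (4.4) set out when tests or screening may be repeated and create no ground for exclusion. Section 5.3 contains no separate discretion clause. The Day 1 procedures (6.3.1) recheck the same criteria before randomization. The SAP adds no eligibility rule.

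6. **The ECG.** Section 8.10 says "A single, standard 12-lead ECG will be performed by the Investigator or trained site personnel at the Screening Visit", with a central reading. SAP Section 3.5.4 summarises PR, QRS, QT and QTcF and the overall interpretation. The only ECG finding tied to an exclusion is ischaemic coronary disease, so a markedly abnormal non-ischaemic tracing has no clear consequence for eligibility.

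7. **Criterion 13 beside Section 4.5.** The entry clause carries the *non-cardiac* limit and the withdrawal clauses do not. The same cardiac condition can support ending participation but does not clearly support refusing entry.

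**The case against.** The strongest reply is that the wording may be deliberate. A sponsor may set its cardiovascular exclusions as a closed list and leave judgement for everything else. The documents neither confirm nor exclude this. That stands, and it is why stating the intent is an acceptable answer. Against it, no rationale is given, criterion 8 shows that at least one non-ischaemic cardiac condition was thought relevant to entry, and Section 4.5 has no matching limit.

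A second reply is that Section 4.5 protects the participant. It is not expressly confined to the period after dosing, and its best-interest ground is broad. This softens the picture of an investigator obliged to dose someone thought unsafe. It remains a withdrawal rule, however, and does not tell a site whom to randomize.

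Three stronger readings are tempting, and the documents do not support them:

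- *That each such withdrawal costs 1 of 25, or 4%, of an arm at Day 57.* Withdrawn participants are not replaced, but one who was dosed and has a baseline LDL-C stays in the mITT Population (SAP 3.2.2). The Early Termination Visit collects a fasting lipid profile (Protocol 6.6), and one falling on Days 44 to 71 is assigned to Day 57 (SAP 3.1.2). The MMRM also uses available Day 29 data (SAP 3.4.1).
- *That pre-existing heart disease would fill the safety tables.* Under Protocol 8.1 a condition present at first dose is medical history unless its severity, frequency or seriousness changes. Safety is summarised descriptively, by arm, with a randomized placebo group.
- *That cardiac discretion matters especially for this drug class.* The protocol's own background points the other way. Section 1.3 reports a thorough QT study with no effect on the corrected interval, Section 1.5 reports no clinically significant vital-sign or ECG effects, and Section 1.1 reports no long-term on-target safety issues with another CETP inhibitor.

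**Conclusion.** The point holds as a minor wording defect. On the natural reading of criterion 13, clinically significant non-atherosclerotic, non-ischaemic heart disease other than torsades meets no exclusion that clearly applies, while Section 4.5 would allow a participant to be discontinued for it.

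The grounds are participant protection and consistent eligibility across sites. Alpha, power and the primary analysis are unaffected. The number of people concerned is probably small. That is a judgement, because the documents give no prevalence. Differing decisions between sites are a possibility that the wording leaves open, not something the documents show will happen.

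The conclusion assumes that *non-cardiac* governs the whole phrase in criterion 13. On the narrower parsing the gap shrinks to an ambiguity, which still needs resolving. A reader might infer that the protocol forbids excluding an unsafe cardiac participant. The text does not go that far: it fails to give that discretion clearly.

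**What to change.** Reconcile criterion 13 with criteria 4 and 8 and with Section 4.5. The simplest way is to remove the qualifier *non-cardiac*, so that the judgement already given to the investigator applies to any clinically significant disease or condition. If the restriction is intended, say so in Section 4.2 and give the reason, so that sites apply it alike.

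No specific cardiac condition or threshold is proposed. Which conditions should bar entry is for the sponsor to decide.

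The cost is a one-word change, or one explanatory sentence, in a protocol amendment. Medical history, physical examination and ECG are already done at Screening (Section 6.2), so no procedure is added, and the SAP needs no change.

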## 4.3 Retesting

If laboratory abnormalities during Screening are considered by the Investigator to be transient, then the laboratory tests may be repeated once during Screening. The Investigator's rationale for retesting should be documented. If the retest result is no longer exclusionary, the participant may be randomized.

#### 4.4 Rescreening

Participants who have screen-failed are permitted to rescreen once, following consultation with the Medical Monitor. Rescreening may be scheduled after at least 5 days have elapsed from the previous study visit.

#### 4.5 Withdrawal Criteria

Participation in this clinical study may be discontinued for any of the following reasons:

- The participant withdraws consent or requests discontinuation from the study for any reason;
- Occurrence of any medical condition or circumstance that exposes the participant to substantial risk and/or does not allow the participant to adhere to the requirements of the protocol;
- Any SAE, clinically significant AE, severe laboratory abnormality, intercurrent illness, or other medical condition which indicates to the Investigator that continued participation is not in the best interest of the participant;
- Pregnancy;
- Requirement of prohibited concomitant medication;
- Participant failure to comply with protocol requirements or study-related procedures; or
- Termination of the study by the Sponsor or the regulatory authority.

If a participant withdraws prematurely from the study due to the above criteria or any other reason, study staff should make every effort to complete the full panel of assessments scheduled for the Early Termination Visit. The reason for participant withdrawal must be documented in the electronic case report form (eCRF).

In the case of participants lost to follow-up, at least 3 attempts to contact the participant must be made and documented in the participant's medical records.

Withdrawn participants will not be replaced.

#### 5 STUDY TREATMENTS

# 5.1 Treatment Groups

Participants will be randomized in a 1:1:1:1 ratio to 1 of the following treatment groups:

- Combination therapy: 5 mg obicetrapib + 10 mg ezetimibe;
- Obicetrapib monotherapy: 5 mg obicetrapib + placebo ezetimibe;
- Ezetimibe monotherapy: placebo obicetrapib + 10 mg ezetimibe; or
- Placebo: placebo obicetrapib + placebo ezetimibe.

# 5.2 Rationale for Dosing

In previous multiple-dose clinical studies of obicetrapib in healthy subjects and patients, near maximal effects were observed with the 5 mg obicetrapib dose. At this dose level, CETP activity and concentrations were effectively reduced, and HDL-C levels were increased while LDL-C levels decreased. According to the Summary of Product Characteristics, the recommended daily dose of ezetimibe is 10 mg. Therefore, the present study will utilize a dose of 5 mg obicetrapib, administered with or without 10 mg ezetimibe, in participants with mild dyslipidemia following the TLC diet.

# 5.3 Randomization and Blinding

Participants who meet all eligibility criteria will be randomized into the study. Participants will be randomized in a 1:1:1:1 ratio to the combination therapy, obicetrapib monotherapy, ezetimibe monotherapy, or placebo treatment groups. At randomization, participants will be stratified according to their Screening Visit (Visit 1) LDL-C value (<3.5 mmol/L [<135 mg/dL] or ≥3.5 mmol/L [≥135 mg/dL]). An automated interactive response technology (IRT) system will be used to assign the participant to 1 of the 4 treatment groups.

Participants, Investigators, the Clinical Research Organization, and the Sponsor will be blinded to all lipid results from Day 1 (Visit 2) for the first participant through the PK Visit (Visit 6) for the last participant in order to protect blinding to treatment assignment.

